#### Hypotheses to be tested:

- 1. We hypothesize that patient- (e.g., health insurance) and provider-level (e.g., patient-provider race discordance) factors are associated with cardiology referral in URM people living with HIV (PLWH) at elevated CVD risk. The primary outcome measure is visit with a cardiologist after meeting criteria for elevated CVD risk.
- 2. We hypothesize that URM PLWH who are seen by a cardiologist will have better CVD outcomes compared to those without referral. Primary outcomes are blood pressure and lipid control, and secondary outcomes are myocardial infarction, stroke, death and cardiovascular death both individually and as a composite, as a function of whether an individual at elevated CVD risk was seen by a cardiologist prior to first event.
  - a. We hypothesize that guideline-directed care including tobacco cessation counseling, cardiac testing, blood pressure and cholesterol medication management, glycemic control and appropriate use of statins mediate the relationship between cardiology referral and CVD outcomes.
- 3. Aim 3 is not driven by a pre-specified hypothesis.

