## 5 Background and Significance

Cardiovascular disease among PLWH disproportionately affects URM populations in the U.S., and is an NIH HIV High Priority Topic of research. Multiple cohort studies have found that HIV infection is associated with increased risk of myocardial infarction, ischemic stroke, and heart failure. The literature shows a 27-75% increased risk for CVD attributable to HIV infection. In addition, PLWH are less likely than uninfected persons to receive treatment and procedures related to CVD. Under-represented racial and ethnic populations in the Southeast "HIV-belt" and "Heart Attack belt" face the highest comorbidity from HIV and cardiovascular disease (CVD) in the nation, accounting for 43% of all new HIV infections and CVD death rates 4x greater than other regions. Despite the benefit of cardiology referral for primary prevention of CVD8, URM are the least likely to be referred to cardiologists when overt CVD exists, 10 or when patients are at high risk for CVD. 12,13. Due to historical stigma, PLWH have been reluctant to engage in medical care outside of their HIV provider. Referral

to cardiology care may benefit PLWH at elevated CVD risk, however, we lack knowledge on the determinants of specialty referral and whether referrals improve cardiovascular outcomes for URM PLWH. The field needs knowledge on the effectiveness of cardiology referrals for URM PLWH. Such evidence will ultimately inform clinical care guidelines and health system interventions to improve health for URM populations with HIV.

Thus, the long-term goal of this proposal is to generate evidence-based recommendations for the management of CVD risk in PLWH. The overall objectives of this application are to demonstrate the effect of cardiology referral on CVD outcomes in a racially/ethnically diverse cohort of PLWH, and to generate qualitative data with which to develop of a future intervention. Our central hypothesis is that cardiology referral reduces incident CVD events in URM populations with HIV compared to non-referral. Our hypothesis has been formulated based on our own work identifying that race and provider specialty impact cardiovascular risk management. The rationale for our research is that, once it is known how health disparity populations with HIV access cardiology referrals, and the impact on CVD outcomes, an intervention can be appropriately designed resulting in new and innovative approaches to the management of URM PLWH at elevated CVD risk.

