#### 7.3.2 Patient EHR data for Exclusion criteria for Aims 1 and 2:

- (1) Age <18 years of age or >99 years of age at index event;
- (2) Pre-existing ASCVD prior to index event, including a previous diagnosis of any acute myocardial infarction, heart failure, acute coronary syndromes, stable or unstable angina, arterial

revascularization (includes coronary arterial or peripheral), stroke, transient ischemic attack or peripheral arterial disease presumed to be of atherosclerotic origin determined by ICD codes;

- (3) Encounter with cardiology specialist within 1 year prior to index
- (4) Evidence of ART for pre-exposure prophylaxis (i.e., Truvada [emtricitabine/tenofovir disoproxil fumarate] or post-exposure prophylaxis (e.g., Truvada plus raltegravir) without HIV diagnosis.

## 7.4 Inclusion and exclusion criteria for Aim 3

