## 12 Data analysis & statistical considerations

#### 12.1 Analysis Plan for Aim 1

For this aim, the primary outcome variable is referral to a cardiology specialist within 6 months of baseline. This will be measured as a binary variable, with 'yes' defined if there is documented evidence that a referral is made within 6 months of becoming eligible by CVD risk score and kept within 3 months of referral, and 'no' otherwise. We will also determine the time from baseline to cardiology referral and the time until the first visit with the cardiology specialist.

We will consider a number of patient and provider factors evaluated at baseline that are potentially associated with referral to a cardiology specialist. Patient factors will include demographic factors (age, sex, race, ethnicity), level of ASCVD risk, Charlson comorbidity index, SES (e.g.; 5 digit zip code, health insurance ([yes/no]), type of health insurance (Medicare, Medicaid, private, Ryan White, etc.), and history of keeping appointments during 2 years prior to baseline. Provider factors will include primary management strategy (coprimary management defined as having both an HIV doctor and Primary Care Practitioner vs. HIV provider as primary care), and years of practice since training. Cardiologist availability will be a site-determined variable. Based on prior literature, we are specifically considering sex as a biological variable that may be related to specialty referral. 

Baseline characteristics of the cohort will be summarized overall and by referral status. We will include the patient and provider factors described above, as well as vital signs (including weight, body mass index and blood pressure), laboratory measures (particularly total and HDL cholesterol, CD4 cell count, HIV viral load), and relevant medications (ART and cardiovascular medications). We will document the patterns of HIV related CVD comorbidity in the study population, as the funding opportunity announcement specified.

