Starting with the population selected for Aim 1, we will create a sub-population by matching patients referred to a cardiology specialist (the primary outcome variable for Aim 1) to similar non-referred patients. The goal of this matching is to balance factors that may be confounders of the relationship between referral and cardiovascular outcomes. We will identify factors found to be associated with cardiology referral from Aim 1, as well as factors that are expected to be associated with outcomes such as, age, race, insurance status/type, ASCVD risk score, and comorbidity index. We will not seek to match on factors that may be associated with referral but unlikely to be directly associated with outcomes. For example, we may not want to match on cardiologist availability by site if this is only related to referral and not independently to outcomes. Variables that potentially modify the effect of referral (e.g., sex, race/ethnicity, insurance status) will be included among the matching factors. Patients will be matched within sites and year of baseline encounter.

For each patient referred to a cardiologist we will identify one non-referred patient (1:1 matching) within each site. We will match using values of the individual confounders, with an exact match on sex, race/ethnicity, insurance status/type, and to within a small caliper for continuous variables (e.g., ±5 years for age). Matched pairs will be identified using optimal matching. If this approach fails to identify an adequate number of matched pairs, then 1:1 matching will be implemented using a propensity score.

Once the matching has been implemented, the same baseline characteristics reported for Aim 1 will be summarized in the matched cohort by referral status. Metrics (e.g., standardized differences) will be reported to evaluate how well-balanced the referred and non-referred groups.

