For this aim, the primary outcome variable will be blood pressure control based on prevailing guidelines during the study period (blood pressure <140/90 mmHg). The co-primary outcome is lipid control, defined by prevailing guidelines during the study period. These outcomes will be evaluated longitudinally during 5-years of follow-up. Secondary outcome variables include time to the first major adverse cardiovascular event (MACE = cardiovascular death, myocardial infarction (MI)), stroke, heart failure hospitalization, peripheral artery disease procedure, coronary artery disease (based on diagnosis codes or coronary artery revascularization procedure), and all-cause death. Events ascertained from relevant diagnosis and procedure codes, and from a query of the National Death Index Plus, State Death records, Social Security Death Masterfile, Hospital death record and/or similar death record for causes of death including cardiovascular

death. We will also evaluate time to BP control and time to lipid control among patients who were not controlled at study start. For this Aim, "time zero" for the matched patient pair will be defined as the time from baseline (see Aim 1) when the referred patient kept their cardiology appointment. Events will be ascertained starting from time zero and until the end of follow-up. For each patient, end of follow-up will be defined as the date of the last outcome event or health system encounter without an event, occurring ≥3 months prior to the retrospective study review period of December 31, 2020 of the EHR.

To evaluate the association between cardiology referral and subsequent blood pressure and lipid control (coprimary outcomes), we will first evaluate these measures between referred and non-referred patients at baseline, and then compare prevalence and time trends between referred and non-referred patients using methods appropriate for longitudinal data analysis. For example, we will explore whether the proportion of patients with adequately controlled BP at each year is higher in referred compared to non-referred patients. Because these analyses are conducted in the matched population, the results are adjusted for the potential confounders included in the identification of the matched pairs.

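### Section 12.2 starts follow-up up to about 9 months after the index-date ASCVD check, with no rule that both members are event-free, or the control still at risk, at that start

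*Combined protocol and SAP*

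**What the plan says.** Section 7.3.2 sets eligibility at index. It excludes "Pre-existing ASCVD prior to index event" and "Encounter with cardiology specialist within 1 year prior to index".

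Section 12.1 counts a patient as referred if "a referral is made within 6 months of becoming eligible by CVD risk score and kept within 3 months of referral"; everyone else is a 'no'.

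Section 12.2 builds the Aim 2 cohort from the Aim 1 population by "matching patients referred to a cardiology specialist (the primary outcome variable for Aim 1) to similar non-referred patients". On timing it adds only this: "Patients will be matched within sites and year of baseline encounter". Time zero for both members "will be defined as the time from baseline (see Aim 1) when the referred patient kept their cardiology appointment", and events are counted from then on. Time to BP control and time to lipid control are analysed in patients uncontrolled at 'study start', a term the section does not define.

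Two other places bear on intent. The Aim 2 hypothesis in Section 4 frames the secondary outcomes by whether the patient was "seen by a cardiologist prior to first event". Section 5 gives the central hypothesis as "cardiology referral reduces incident CVD events in URM populations with HIV compared to non-referral".

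**The concern.** Eligibility is fixed at index but the clock starts months later, and nothing is checked again in between. Four things can follow if the plan is carried out as written.

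- A patient has an MI or stroke after index, is referred because of it, keeps the visit and enters as referred. A later event is then analysed as the first.
- A control has a non-fatal event before the pair's time zero, and a later event is again analysed as the first.
- A control dies or leaves care before time zero. Follow-up then ends before it begins, and the plan does not say what happens to the pair.
- A control sees a cardiologist before time zero but keeps the 'no' label, because there was no documented referral, the visit came more than 3 months after referral, or the referral came after month 6.

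The first two conflict with a hypothesis about incident events. A related ambiguity is 'study start': if it means baseline, patients who reached control between baseline and time zero enter the time-to-control analyses with the outcome already met.

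**Working it through.** **Inputs.** From Section 12.1: referral within 6 months, kept within 3 months. From Section 12.2.1: MACE about 5% at 5 years; 300 per group as the power example; referral rate 20-25%; control rates of 30% (BP) and 45% (lipids), with increases of 10 and 15 points. Two-sided 0.05.

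**The plan's own figures.** Two-proportion power with 300 per group is 72.9% for 30% vs 40% and 95.9% for 45% vs 60%. These agree with the stated >70% and >95%.

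**Length of the gap.** The maximum is 6 + 3 = 9 months. The documents give no distribution. If referral is uniform over months 0-6 and the visit uniform over the next 3 months (assumption), the mean is 3 + 1.5 = 4.5 months. If the 12-month sensitivity analysis is carried into Aim 2 with the 3-month rule kept (assumption), the maximum is 15 months.

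**Events in the gap if events do not prompt referral.** With a constant hazard, h = -ln(0.95)/5 = 0.01026 per year and P(event by t) = 1 - exp(-h t).

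| Gap | P(MACE before time zero) | Per 300 |
|---|---|---|
| 4.5 months (assumed mean) | 0.38% | 1.2 |
| 9 months (maximum) | 0.77% | 2.3 |
| 15 months (sensitivity analysis maximum) | 1.27% | 3.8 |

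For comparison, expected MACE per 300 is 300 x 0.05 = 15 at 5 years and 300 x [1 - exp(-8h)] = 23.6 at 8 years. The 1.2 to 2.3 patients equal 8-15% of the 5-year count or 5-10% of the 8-year count.

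Pairs with at least one member affected number 300 x [1 - (1 - p)^2], which is 2.3 at the mean gap and 4.6 at the maximum.

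**Events in the gap if events do prompt referral.** The documents give no rate, so this is a range under assumption. It was simulated with 8 million patients. A share of events in months 0-6 leads to a kept referral, the routine referral rate is 20-25%, and all events are treated as survivable.

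| Share prompting referral | Referred, per 300 (22% routine) | Controls, per 300 (22%) | Pairs affected, per 300 (22%) |
|---|---|---|---|
| 25% | 2.5 | 0.9 | 3.4 |
| 50% | 3.9 | 0.6 | 4.5 |
| 80% | 5.4 | 0.3 | 5.7 |
| 95% | 6.2 | 0.1 | 6.3 |

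Over routine rates of 20-25% the referred count runs from 2.3 to about 6.9 and the pairs affected from 3.1 to 7.0.

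**Room in the co-primary power.** With pairs removed, BP power is 71.9% at 293, 70.1% at 281 and 69.97% at 280. Lipid power is 95.5% at 293, 95.06% at 286 and 94.995% at 285. Both stated figures therefore hold down to 286 pairs, a margin of 300 - 286 = 14.

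**The case against.** The strongest reply is that the plan already covers the referred arm. The Section 4 hypothesis requires the visit to precede the first event, Section 12.2 speaks of time to the first MACE, and a control whose follow-up ended before time zero adds no person-time to a Cox model. Part of this stands. Section 4 shows the intent, and a control who died early would drop out of the model. But Section 4 states a hypothesis that Section 12.2 does not turn into a selection rule, it sets no condition on the control, and events are ascertained only from time zero. Controls with earlier non-fatal events and the handling of broken pairs remain open. The routine-follow-up sensitivity analysis carried over from Aim 1 deals in part with patients who left care, not with earlier events.

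The second reply is that the effect is small and that the larger counts rest on an assumed share. This stands. MACE also includes cardiovascular death, and a patient who has died cannot keep a visit, so the upper end is too high for MACE alone.

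The third reply is that 'study start' may already mean time zero, which the next sentence defines. That reading is plausible, but the text does not settle it.

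A reader might also infer that the referred member could be dead or out of care at time zero, or that the referred group gains immortal time. The documents do not support either. Time zero is a visit the referred patient kept, and both members' clocks start there. The shared start is sound.

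**Conclusion.** The concern holds as an omission from Section 12.2 that should be fixed. Event-free status at time zero is unguarded for both members; being alive, in follow-up and not yet seen by cardiology is unguarded for the control only.

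The effect falls on the secondary time-to-event analyses, including time to control if 'study start' means baseline. On the plan's own rate it is small: 1.2 to 2.3 per 300 per group, assuming a constant hazard and a gap of 4.5 to 9 months. It becomes larger and unbalanced only if events prompt referral. Other Aim 2 events, controls already seen by cardiology, and early BP or lipid control cannot be sized from the documents.

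A reader might infer that the yearly BP and lipid comparisons are compromised, or that the bias favours one group. Neither is shown: no claim is made about those comparisons, and the net direction is unknown.

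**What to change.** In Section 12.2, keep the existing matching rules and add the following.

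1. Select each control from patients who, at the same time since index as the referred patient's visit, are alive, in follow-up and without a post-index cardiology visit.
2. For the event analyses, require both members to be free at time zero of the ASCVD conditions listed in Section 7.3.2 and of the Aim 2 event outcomes. Exclude referred patients whose first event precedes the visit. Both lists are needed, because Section 7.3.2 includes conditions that are not Aim 2 outcomes, such as transient ischaemic attack.
3. State that 'study start' for time to BP and lipid control is time zero.

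Limiting item 2 to the event analyses keeps its exclusions out of the yearly BP and lipid comparisons. This matters because lipid power has a margin of only 14 pairs and the full number of exclusions is unknown.

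The cost is wording, some matching code, and usable visit, event and death dates; Section 8.1 leaves data availability open. The event analyses would lose about 2 to 7 of 300 pairs counting MACE only (2.3 with no prompting at the mean gap, 7.0 at 20% routine referral and a 95% share). The loss from other conditions cannot be sized. Item 1 narrows the control pool for all Aim 2 analyses by an unknown number, although a control who fails it can be replaced where another match exists.

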## 8 Study Procedures

## 8.1 Aims 1 and 2 Study Procedures

We will analyze patient-level and provider-level data from electronic health records (EHRs) from STAR Clinical Research Network (CRN) institutions using CDM. These institutions include Duke University Health System, Vanderbilt Universities, and Medical University of South Carolina.

We (DCRI CC) will retrospectively ask the DataMarts to query the EHR for eligible patients based on age, race, ethnicity, and HIV diagnosis to identify Black/African-American and other URM PLWH. Additional data that are already collected as part of routine medical care will be extracted by sites

from patient EHRs starting at the first clinical contact after January 1, 2010, to create a contemporary cohort with at least 5 years of longitudinal follow-up data. Longitudinal follow- up data will be collected through December 31, 2020. Data will be reviewed and or collected from patient EHR from January 1, 2010 through December 31, 2020. Patients will be included for analysis in this retrospective study at the time of the first clinical encounter during an ("eligibility period") when they meet the inclusion/exclusion criteria (listed below), with a "look back period" of 1 years prior to "enrollment" (i.e., back as far as 2010) to establish medical history and other baseline factors. These dates may be adjusted during the course of the study depending on availability of data in the various DataMarts. The overall scientific premise is depicted in Section 8.2 which shows our approach without specific dates.

DataMarts, Site PIs and Site study teams will link local EHR records with death events and cause of death prior to sending the final dataset to the DCRI CC. Sites will query and link records using National Death Index Plus, State Death records, Social Security Death Mastefile, Hospital death record and/or similar death record for causes of death including cardiovascular death, retaining protected health information needed to query these databases at the site level.

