To evaluate the association between cardiology referral and CVD events (secondary outcomes), the cumulative incidence of primary and secondary outcomes will be summarized in the referred and matched non-referred patients. Follow-up will be censored at the earliest of 8 years or end of follow-up. For each outcome variable a Cox regression model will be fit, and the hazard ratio (referral vs. not referred) and 95% CI, and p-value will be reported. The Cox regression analysis will account for the matched pairs design using the empirical sandwich variance estimate. Statistical significance will be determined at the two-sided 0.05 level.

The relationship between referral status and outcomes will also be evaluated within subgroups of primary interest: sex, race, ethnicity and insurance as defined in Aim 1. Evidence for a differential association between referral status and CVD outcomes for different subgroups will be quantified using an interaction test in the Cox regression analysis. The considerations and approaches outlined in Aim 1 regarding missing data and sensitivity analyses will also be applicable for Aim 2.

#### 12.2.1 Expected power and sample size for Aim 2

Aim 2 expected power and sample size: With an anticipated cardiology referral rate of 20-25% among 1,200-1,500 patients included in Aim 1, the sample size in the matched cohort study is expected to be 250-375 per group. These patients will be accrued into the study over 5 years (2012-2016) and then followed to evaluate BP and lipid control, and for cardiovascular events for up to 8 years through December 31, 2020. For the primary endpoints, the rates in the non-referred group are anticipated to be 30% and 45% for BP and lipid control, respectively. With 300 per group, the study is predicted to have >70% power to detect a 10% increase in rate of BP control, and >95% power to detect a 15% increase in rate of lipid control due to cardiology referral. For the secondary endpoints, the rate of MACE events is anticipated to be fairly low (i.e., a cumulative incidence ~5% at 5 years and ~10% at 10 years) and we anticipate modest power to detect even large reductions in risk of CVD events due to cardiology referral. However, this aim will provide useful information about clinical event rates and estimates of the potential to effect event rates that could be attributed to cardiology referral.

#### 12. 3 Analysis Plan for Aim 3

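### Where outside death linkage is substantially complete, the end-of-follow-up rule counts time out of care only if it ends in death: mortality is overstated, and the death hazard ratio is materially biased if retention differs by referral group

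*Combined protocol and SAP*

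**What the plan says.** Section 12.2 defines when observation stops: "For each patient, end of follow-up will be defined as the date of the last outcome event or health system encounter without an event". The date must lie at least three months before 31 December 2020. The event analyses then use it: "Follow-up will be censored at the earliest of 8 years or end of follow-up". Two kinds of result depend on it. One is descriptive, since "the cumulative incidence of primary and secondary outcomes will be summarized in the referred and matched non-referred patients". The other is a Cox hazard ratio for each outcome. All-cause death is a named secondary outcome, and cardiovascular death is part of MACE and is also listed individually in the hypotheses of Section 4.

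Deaths are not limited to those seen in the health system. Section 8.1 says "DataMarts, Site PIs and Site study teams will link local EHR records with death events and cause of death", and "Sites will query and link records using National Death Index Plus", with state records, the Social Security file and hospital records as further options. Section 12.2 repeats the list, ending "Hospital death record and/or similar death record for causes of death". The list is permissive: it does not say which site uses which source, or how complete the capture is. Neither section gives death a censoring date of its own.

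**The concern.** A national or state death file can record a death years after a patient's last visit. Under the rule, that death is the last outcome event, so it sets the end of follow-up and the months or years before it count as time at risk. A patient who left care on the same day and is still alive has no event and stops at the last visit. Whether out-of-care time enters the analysis therefore depends on how it ends. Linked deaths stay in the numerator while survivors' time leaves the denominator.

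What is at stake is the reported cumulative incidence of death and, if the referred and non-referred groups leave care at different rates, the death hazard ratio. Unequal retention is plausible from the design: the referred patient has a visit at time zero by definition, while the matched patient needs none. Against that, "history of keeping appointments during 2 years prior to baseline" is a referral factor in Section 12.1 and so a candidate for matching. The documents give no retention data, so neither the size nor the direction of any gap is known.

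**Working it through.** **Figures in the plan.** The plan has no mortality, retention or capture figure to reproduce. The nearest is the MACE rate in Section 12.2.1, about 5% at 5 years and 10% at 10 years. These agree with each other: a constant hazard h = -ln(0.95)/5 = 0.01026 per year gives 1 - exp(-10h) = 9.75% at 10 years.

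**Inputs from the documents.** Accrual 2012-2016. Time zero up to 9 months after baseline (6 months to referral plus 3 months to the visit, Section 12.1). Data end 30 September 2020. Cap at 8 years. 300 per group.

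**Assumptions.** True five-year mortality 5.0%. Permanent loss from care of 5%, 10% or 15% a year. The share of out-of-care deaths captured, and the death risk after leaving, are both varied.

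**Hand check.** At time t let S be the share alive, R the share still in care and F the chance that a living patient dies before data end. The true risk set is S. Under the rule, with full linkage, it is S × [R + (1 - R) × F], while every death still counts. Take 10% loss at t = 2.5 years. Average time to data end is 8.75 - 2.875 = 5.875 years, which leaves 3.375 years.
- R = 0.9^2.5 = 0.768
- F = 1 - exp(-0.01026 × 3.375) = 0.034
- Bracket = 0.768 + 0.232 × 0.034 = 0.776
- Apparent hazard = 0.01026 / 0.776 = 0.01322
- Five-year mortality = 1 - exp(-5 × 0.01322) = 6.4%, against a true 5.0%

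**Simulation** (3,000,000 per group; Kaplan-Meier at 5 years; loss 5/10/15% a year):

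| Death risk after leaving | Out-of-care deaths captured | Truth, % | As written, % | Survivors censored at common date, % |
|---|---|---|---|---|
| Unchanged | 100% | 5.0/5.0/5.0 | 5.7/6.4/7.5 | 5.0/5.0/5.0 |
| Unchanged | 50% | 5.0/5.0/5.0 | 5.3/5.7/6.3 | 4.7/4.4/4.2 |
| Unchanged | 0% | 5.0/5.0/5.0 | 5.0/5.0/5.0 | 4.4/3.9/3.4 |
| Doubled | 100% | 5.6/6.1/6.5 | 6.3/7.8/9.8 | equals truth |
| Doubled | 50% | 5.6/6.1/6.5 | 5.6/6.5/7.5 | 5.0/5.0/5.0 |
| Doubled | 25% | 5.6/6.1/6.5 | 5.3/5.7/6.3 | 4.7/4.4/4.2 |
| Doubled | 0% | 5.6/6.1/6.5 | 5.0/5.0/5.0 | 4.4/3.9/3.4 |

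If leavers can return, the error shrinks. With unchanged risk and full capture, mortality reads 5.3/5.7/6.1% if half return and 5.2/5.3/5.4% if 80% return.

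**Death hazard ratio**, true value 1.00, full capture, loss in referred/non-referred: 5/5 and 10/10 give 1.00; 5/7.5 gives about 0.93; 5/10 gives 0.85 (0.92 if half of leavers return); 10/5 gives about 1.17. A common date gives 1.00 throughout. With equal retention and a real effect there is a slight pull toward 1. Over five-year mortality of 5-20% and loss of 5-20% a year, 0.70 becomes 0.701-0.716 and 0.50 becomes 0.501-0.520.

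**Composite**, true 5.0%: 5.1/5.3/5.5% if 20% of events are fatal, and 5.4/5.8/6.3% if 50% are.

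**Sampling error for scale.** About 17.5 deaths per 300 gives a 95% interval around 1.00 with factor exp(1.96 × √(2/17.5)) = 1.94, that is 0.52 to 1.94. For a 5% rate the half-width is 1.96 × √(0.05 × 0.95/300) = 2.5 points.

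**The case against.** The strongest reply has four parts.

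- **Direction.** A reader might infer that mortality is always overstated, or that sites with only in-system deaths are free of error. Neither holds generally. With doubled death risk after leaving, 10% loss and 25% capture, a true 6.1% reads 5.7%. An in-system-only site reads 5.0% against the same 6.1%. Both statements need conditions, and the documents fix neither the capture nor the risk after leaving.
- **Remedy.** A common censoring date applied everywhere could do more harm than the present rule. At 10% loss and doubled risk, 50% capture reads 5.0% with a common date and 6.5% as written, against a true 6.1%. The capture at which the two rules err equally is about 43% with unchanged risk and 64% with doubled risk. This stands, and it limits where a common date may be used.
- **Existing safeguard.** Section 12.1 plans a re-analysis restricted to patients in routine follow-up, and Section 12.2 extends it to Aim 2. It helps only if its unstated threshold is strict. At 10% loss, requiring two years of retention leaves 5.5%, and at 5/10 loss a hazard ratio of 0.93; requiring five years leaves 5.0% and 0.99. The main rule is unchanged either way.
- **Materiality.** These are secondary outcomes, Section 12.2.1 already expects modest power for them, and chance alone spans 0.52 to 1.94. With one group of 300, only loss near 15% a year produces an error as large as the sampling half-width. This stands and keeps the point minor. It does not remove it, because the bias does not shrink with sample size and the death results will be reported.

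A reader might also infer that the hazard ratio is tilted in favour of referral. That would need better retention among referred patients, which the documents do not show; the opposite gap gives about 1.17.

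**Conclusion.** The rule is wrong as written, at minor severity. It treats leavers who die and leavers who survive differently wherever deaths are found outside the health system. Where that linkage is substantially complete, all-cause and cardiovascular mortality are overstated: by about 0.7, 1.4 and 2.5 points on a true 5.0% at 5%, 10% and 15% annual loss with full linkage, permanent departure and unchanged risk. With low capture and raised risk after leaving, the error can be downward. Sites with in-system deaths only are unbiased only if leaving care is unrelated to death risk.

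The death hazard ratio is materially affected only if retention differs by referral group; with equal retention the shift is at most about 0.02. Composites containing death are affected less. The co-primary blood pressure and lipid outcomes are not affected, nor is the power stated for them. Every rate used is an assumption. What rests on the documents is the asymmetry itself and the absence of a separate censoring date for death.

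**What to change.** In Section 12.2:

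1. Record each site's death sources and the date through which linkage is complete.
2. For all-cause and cardiovascular death at sites with near-complete outside linkage (for example, a National Death Index Plus search of the whole cohort), censor every survivor at that date, or at 8 years if earlier, regardless of the last encounter.
3. At sites with partial linkage or hospital records only, and for composites everywhere, use one symmetric rule. End follow-up for everyone at the last encounter plus a short window fixed in advance, and count no event after it, deaths included. State that this assumes leaving care is unrelated to death risk.
4. Report retention by referral group and, as a sensitivity analysis, deaths under the other censoring rule.

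Because "Patients will be matched within sites and year of baseline encounter", both members of a pair fall under the same rule. A pooled incidence would still mix two rules, which the sensitivity analysis makes visible.

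The cost is a few sentences, a derived censoring date, a retention table and linkage information from the sites. There are two downsides. Under (3) some late linked deaths drop out, and the window slightly undercounts: with visits every 3 or 6 months and a 6-month window, a true composite rate of 5.0% reads 4.8-4.9%, against 5.2-6.7% under the present rule. Rule (2) undercounts if linkage is incomplete: at 10% loss and 50% capture a true 5.0% reads about 4.4%, and with doubled risk a true 6.1% reads about 5.0%. It must not be used at sites with partial linkage.
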